Although Hallux Valgus is a common problem presenting to the foot and ankle surgeon, many aspects of this disease entity are still poorly understood. Surgical procedures are plenty, and can be very broadly classified into those that correct the deformity via soft tissue reconstruction and those that correct through osteotomies. There is currently no gold standard surgical procedure that is proven to be the most superior and lots of exciting research is being undertaken globally. The commonest distal soft tissue procedure is the McBride operation where the tight lateral tissues such as the adductor hallucis and lateral capsule are released while the lax medial capsule is plicated and a bunionectomy is performed. Upon this theoretical background, multiple modifications of the original procedure have been proposed, from double skin incisions to endoscopic variants.

Many patients feel that the restriction of weight bearing immediately after surgery an obstacle to their activities of daily living (ADL) and one of the chief determining factors to undergo surgery or not. Rehabilitation plans vary even amongst pure distal soft-tissue procedures, with some units allowing immediate post-operative weight bearing, while others having a 12-week

period of post-operative non-weight bearing walking. Not critical evidence is available to account for the discrepancies but a prolonged period of non-weight bearing is usually employed in the fear that the construct will fail and early recurrence will occur if stressed too early.

To the best of our knowledge, there has been no trial to investigate the optimal timing to allow weight bearing walking after distal soft tissue reconstruction for hallux valgus. This article will investigate if early weight bearing will affect the outcomes for patients whom have underwent Endoscopic Assisted Distal Soft Tissue Procedure (EDSTP). This procedure is chosen because the it is a minimally invasive modification of the McBride procedure and has one of the longest publishing track records. It is the default procedure of choice in the investigators' institution; with the current post-operative protocol requiring the patient to undergo a 6-week period of non-weight bearing walking before initiating heel walking at 6 weeks.

Hypothesis and study objectives

The objective of the randomized controlled trial is to investigate whether early partial weight bearing will improve the outcomes of patients undergoing EDSTP.

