We hypothesize that compared with standard 6-week non-weight bearing, early partial weight bearing walking at 2 weeks post-surgery improves the patient's quality of life, allows faster rehabilitation with better 1MTPJ range of motion and faster decrease in generalized swelling. This early weight bearing rehabilitation program will not negatively affect the stability of the surgical reconstruction correction and maintains a good radiological outcome as well as the traditional rehabilitation protocol where weight bearing begins at 6 weeks.

Patients and Methods

Patients

This is an open-label randomized controlled trial. We aim to recruit 50 adult (>18 yrs) patients who undergo hallux valgus by the EDSTP will be recruited. Exclusion criteria are those whom have disabilities (both physical and mental) which may impair the adherence of the rehabilitation and those who have undergone additional procedures such as concomitant 2nd toe deformity correction.

Randomization will be performed after the end of the EDSTP surgery to ensure there is no bias during the surgical procedure. Parallel groups will be allocated at 1:1 ratio via a computer generated random number, with 25 patients at each group.

In the control group, the subjects will follow the existing rehabilitation protocol of non-weight bearing walking for 6 weeks followed by heel walking for 6 weeks, followed by the resumption of normal full weight-bearing walking in normal shoes at 12 weeks post-operation. In the trial group, the subjects will begin heel walking when the bulky dressing and sutures are removed at 2 weeks post-operation and resume full weight bearing walking in normal shoes at 12 weeks post-operation. All subjects will be followed-up at 2 weeks, 6 weeks, 12 weeks, 18 weeks and 26 weeks post-operatively.

This study will be performed in the North District Hospital in Hong Kong. The study protocol will be approved by the Joint Chinese University of Hong Kong – North Territories East Cluster Clinical Research Ethics Committee and all participant will provide written informed consent. The study procedure will be conducted in compliance with Declaration of Helsinki and Good Clinical Practice (GCP) Guidelines.

Study outcomes

The primary outcomes are:

- Radiological changes including hallux valgus angle (HVA), intermetatarsal angle (IMA), and tibial sesamoid position by weight bearing feet X-Rays will be measured at 12, 18, and 26 weeks post-surgery.

Secondary Outcomes are:

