- Pain at the bunion, the first metatarsophalangeal joint (1MTPJ) and transfer metatarsalgia using the visual analogue scale will be measured at 2, 6, 12, 18, and 26 weeks post-surgery.
- Range of Motion (ROM) at 1MTPJ will be measured at 2, 6, 12, 18, and 26 weeks post-surgery.
- Foot function measured by the American Orthopaedic Foot and Ankle, Score hallux score, which ranges from 0 to 100, will be conducted at 12, 18, and 26 weeks post-surgery.
- Foot function by the self-reported Foot and Ankle Outcome Score (FAOS) questionnaire will be measured at 12, 18, and 26 weeks post-surgery. FAOS consists of 5 subscales: pain, other Symptoms, function in ADL, function in sport and recreation, and foot and ankle-related Quality of Life. The previous week is taken into consideration when answering the questionnaire. Standardized answer options are given (% Likert boxes) and each question gets a score from 0 to 4. A normalized score (100 indicating no symptoms and 0 indicating extreme symptoms) is calculated for each subscale.

Statistical analysis

All analyses will be performed in IBM SPSS Statistics, Version 20.0 (SPSS Inc, Chicago, IL, USA). Results are shown as mean \pm SD, median (interquartile range) or number (frequency) depending on the type and distribution of data. Between-group comparisons will be conducted by one-way analysis of variance (continuous normal distributed data), Mann-Whitney U test (continuous non-normally distributed data), or chi-square test (categorical data) depending on the type and distribution of data. All hypotheses are two-tailed, and p values <0.05 are considered statistically significant.

References

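### FAOS starts at week 12, six weeks after the two walking regimens become the same, so a short-lived early gain in quality of life or daily function would go unrecorded; the hypothesised swelling benefit has no listed outcome

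*Combined protocol and SAP*

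**What the plan says.** The Introduction motivates the trial by the burden of restriction soon after the operation: "Many patients feel that the restriction of weight bearing immediately after surgery an obstacle to their activities of daily living (ADL". The Hypothesis section predicts better quality of life with walking from week 2, and adds that the early programme "allows faster rehabilitation with better 1MTPJ range of motion and faster decrease in generalized swelling".

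Under Patients, the control regimen is "non-weight bearing walking for 6 weeks followed by heel walking for 6 weeks", with full weight bearing from week 12. The trial arm starts heel walking at week 2 and also moves to full weight bearing at week 12. On visits: "All subjects will be followed-up at 2 weeks, 6 weeks, 12 weeks, 18 weeks and 26 weeks post-operatively".

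Under Study outcomes, the secondary outcomes are scheduled as follows.

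- FAOS, with five subscales that include daily-living function and quality of life: "Foot function by the self-reported Foot and Ankle Outcome Score (FAOS) questionnaire will be measured at 12, 18, and 26 weeks post-surgery". On recall: "The previous week is taken into consideration when answering the questionnaire".
- AOFAS hallux score: "which ranges from 0 to 100, will be conducted at 12, 18, and 26 weeks post-surgery".
- Range of motion: "Range of Motion (ROM) at 1MTPJ will be measured at 2, 6, 12, 18, and 26 weeks post-surgery". Pain has the same five time points.

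No primary or secondary outcome is identified as swelling.

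**The concern.** The trial is motivated by how patients live in the first weeks after surgery, and the prescribed contrast lasts only for some of those weeks. The one instrument that measures quality of life and daily function is held back until both arms have been on the same regimen for several weeks. If early walking helps while it lasts and the arms then draw level, the trial will have no record of it. A reader of a null FAOS result at week 12 could conclude that early walking brings no quality-of-life gain, when the question was not asked at the relevant time. Week-6 responses cannot be recovered afterwards.

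Swelling is a separate and smaller gap: the hypothesis makes a claim that no listed outcome is set up to test.

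**Working it through.** The plan gives no effect size, SD, power or attrition figure, so there is no stated calculation to reproduce. The check is mainly one of timing.

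**Timing** (inputs from Patients and Study outcomes)

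- Period of difference: trial arm changes at week 2, control arm at week 6, so 6 − 2 = 4 weeks.
- From convergence to the first FAOS: 12 − 6 = 6 weeks. With one-week recall, the window opens at week 11, which is 11 − 6 = 5 weeks after convergence.

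| FAOS visit | Recall window | Overlap with weeks 2-6 |
|---|---|---|
| Week 12 | weeks 11-12 | none |
| Week 18 | weeks 17-18 | none |
| Week 26 | weeks 25-26 | none |
| Week 6 (not planned) | weeks 5-6 | the full week |

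So 0 of 3 planned FAOS assessments fall in the period of difference. Adding AOFAS, 0 of 6 function-score assessments come before week 12. Pain and range of motion each have 2 of 5 assessments at weeks 2 and 6. Only week 6 is informative about the regimens, because the trial arm is just starting to heel walk at week 2.

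**What the sample could show** (inputs: 25 per arm and two-sided 0.05 from the protocol; effects in SD units are assumptions)

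The detectable difference solves power = 0.80 for a two-sample t-test, which is one-way ANOVA with two groups.

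- Normal approximation: (1.960 + 0.842) × √(2/25) = 0.79 SD. Exact noncentral t: 0.81 SD.
- Mann-Whitney, assuming relative efficiency 0.955: about 0.83 SD.
- Assumed loss of 12% (25 × 0.88 = 22 per arm): 0.86 SD. Assumed loss of 20% (25 × 0.80 = 20 per arm): 0.91 SD.
- 95% confidence interval half-width: t(0.975, 48) × √(2/25) = 2.011 × 0.283 = 0.57 SD.

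Chance of a significant result with 25 per arm (t-test):

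| Assumed week-6 difference | Measured at week 6 | Week 12, half remains | Week 12, none remains |
|---|---|---|---|
| 0.8 SD | 79% | 28% (0.4 SD) | 5% |
| 0.5 SD | 41% | 14% (0.25 SD) | 5% |

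The 5% column is the false-positive rate alone.

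**Number of comparisons.** Planned FAOS: 5 subscales × 3 visits = 15. Adding two subscales at week 6 gives 17; adding all five gives 20.

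**The case against.** The best counter-argument is that the hypothesis gives no time point for quality of life. The notion of speed is attached to rehabilitation and swelling, so comparing FAOS at weeks 12 to 26 is a legitimate test of the sentence as written. This is a choice about when to measure a secondary outcome, not a contradiction. That stands, and it is why the point is limited to a transient benefit. It does not remove the gap, since the Introduction places the burden in the early period.

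Second, a week-6 daily-living score would partly restate the allocation, because control patients have been told not to bear weight, and the trial is open-label with self-report. This also stands. It applies less to the Quality of Life subscale, and the size of that burden is what the rationale concerns. Open-label self-report already affects FAOS at the later visits.

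Third, the added comparison would be imprecise, and giving five subscales while comparing two could look selective. The imprecision is real, though an estimate with its interval is better than none. Naming the two subscales in advance, because they match the hypothesis, answers the charge of selection.

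Fourth, the protocol gives no visit windows, so a late 6-week visit could bring heel-walking days into the control arm's recall. That is correct, and the fix has to deal with it.

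Finally, FAOS has a subscale for other symptoms whose items the protocol does not list, so it might touch on swelling. Even so, it starts at week 12 and could not show a faster early decrease.

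**Conclusion.** The concern holds. FAOS and AOFAS both miss the only four weeks in which the prescribed regimens differ, and no listed outcome is identified as swelling. What is lost is any quality-of-life or daily-function gain that has faded by weeks 11-12; a gain that lasts could still be detected, and early pain and range of motion are covered at week 6. The timing result rests only on the protocol's own weeks and recall period, and assumes patients follow the prescribed regimens. The power figures are illustrative, on assumed effects, and the finding does not depend on them. The primary radiological comparison is untouched, so this is a change that should be made rather than a fault that undermines the trial.

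**What to change.** Add FAOS at the existing 6-week visit. State that it is completed before control patients begin heel walking, and record the completion date so that late forms can be identified. Pre-specify the daily-living and Quality of Life subscales at week 6 as a secondary comparison, reported as a mean difference with 95% confidence interval, with weeks 12, 18 and 26 as later follow-up. Say in the plan that the week-6 daily-living score partly reflects the control arm's restriction. A week-2 FAOS is optional. It would precede the divergence of regimens but follow both surgery and randomisation, so it should not be called a baseline.

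For swelling, either add a foot circumference measurement at the existing visits or take swelling out of the hypothesis.

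The cost is a few minutes of patient time at a visit already scheduled, plus a brief tape measurement if that option is chosen. Some sport items may be unanswered while activity is restricted. FAOS comparisons rise from 15 to 17, and only differences of about 0.8 SD would be detected with 80% power. No visit or treatment changes.

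### No outcome has a listed pre-operative value and no baseline-adjusted analysis is planned; FAOS and AOFAS, first measured at week 12, lose most by it

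*Combined protocol and SAP*

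**What the plan says.** Under Study outcomes, the FAOS "questionnaire will be measured at 12, 18, and 26 weeks post-surgery", and the AOFAS hallux score, "which ranges from 0 to 100, will be conducted at 12, 18, and 26 weeks post-surgery". The FAOS gives five separately normalised scores: "FAOS consists of 5 subscales: pain, other Symptoms, function in ADL, function in sport and recreation, and foot and ankle-related Quality of Life".

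Pain at three sites starts earlier, the last of them being "transfer metatarsalgia using the visual analogue scale will be measured at 2, 6, 12, 18, and 26 weeks post-surgery". So does joint motion: "Range of Motion (ROM) at 1MTPJ will be measured at 2, 6, 12, 18, and 26 weeks post-surgery". The primary radiographic measures, ending with "tibial sesamoid position by weight bearing feet X-Rays will be measured at 12, 18, and 26 weeks post-surgery", are described as changes, yet no pre-operative film is listed. The visit schedule under Patients is entirely post-operative: "All subjects will be followed-up at 2 weeks, 6 weeks, 12 weeks, 18 weeks and 26 weeks post-operatively".

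The same section places randomisation after the end of surgery, 1:1 with 25 per arm. No stratification is mentioned and eligibility sets no severity limits. The trial arm starts heel walking at 2 weeks and the control arm at 6 weeks; both return to normal shoes at 12 weeks.

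Statistical analysis names one-way ANOVA, the Mann-Whitney U test and the chi-square test for between-group comparisons, two-sided at 0.05. It mentions no covariate and no change score.

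**The concern.** How well a patient functions months after bunion surgery plausibly depends in part on how disabled the patient was beforehand. Without severity limits that starting level may vary widely, and with 25 per arm and no stratification the arms can differ on it by chance.

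As planned, each arm's post-operative scores are compared raw. A reader of the results could not check whether the arms began alike on function, could not see how far patients improved from their pre-operative state, and could not adjust for the patient's own starting score. This touches a stated aim: quality of life is the first benefit named under Hypothesis and study objectives, and the FAOS quality-of-life subscale is the only listed outcome labelled as measuring it. Precision is also given up in a small trial, where a covariate costs much less than extra patients.

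**Working it through.** **Plan's own figure.** The sample size is 50, as 25 + 25. The plan gives no effect size, SD, power or dropout rate, so it cannot be reproduced further.

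**Counting comparisons** (scores × visits, from Study outcomes). One test per score per visit is an assumption, because the plan names no test time point.

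- Pain VAS: 3 sites × 5 visits = 15
- Range of motion: 1 × 5 = 5
- AOFAS: 1 × 3 = 3
- FAOS: 5 subscales × 3 visits = 15
- Total secondary: 15 + 5 + 3 + 15 = 38; FAOS plus AOFAS: 15 + 3 = 18
- Primary radiographs: 3 measures × 3 visits = 9

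None of the 38 + 9 = 47 has a listed pre-operative value. What sets the 18 apart is that pain and range of motion have a week-2 value, taken at about the time the regimens diverge, whereas FAOS and AOFAS have nothing before week 12.

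**Chance imbalance at 25 per arm** (normal approximation, in baseline SD units).

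- Standard error of a baseline difference = √(2/25) = 0.283
- P(difference beyond ±0.3 SD) = 2 × [1 − Φ(0.3/0.283)] = 0.289
- P(difference beyond ±0.5 SD) = 2 × [1 − Φ(0.5/0.283)] = 0.077

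**What an imbalance does to an unadjusted test when the regimens are equivalent.** Let r be the baseline-outcome correlation and d the baseline gap, both variables in SD units. Given d, the outcome difference has mean r × d and SD 0.283 × √(1 − r²). The test rejects beyond 1.96 × 0.283 = 0.554.

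| Gap d | r | Shift r × d | Conditional SD | Conditional false-positive rate |
|---|---|---|---|---|
| 0.3 | 0.3 | 0.09 | 0.270 | 5.1% |
| 0.3 | 0.5 | 0.15 | 0.245 | 5.1% |
| 0.5 | 0.3 | 0.15 | 0.270 | 7% |
| 0.5 | 0.5 | 0.25 | 0.245 | 11% |

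Averaged over all possible gaps, the rate is 5%.

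**Gain from adjustment.** The residual variance factor is 1 − r², the equivalent n per arm is 25/(1 − r²), and the difference detectable with 80% power is (1.96 + 0.84) × 0.283 × √(1 − r²). Power for a 0.5 SD difference is Φ(0.5/[0.283 × √(1 − r²)] − 1.96).

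| r (assumed) | Variance cut | Equivalent n per arm | Detectable difference | Power at 0.5 SD |
|---|---|---|---|---|
| 0 (unadjusted) | 0 | 25 | 0.79 SD | 42% |
| 0.3 | 9% | 27.5 | 0.76 SD | 46% |
| 0.5 | 25% | 33.3 | 0.69 SD | 53% |

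These figures ignore the one degree of freedom spent on the covariate. The documents give no correlation, so the range stands in for it.

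**The case against.** The strongest reply is that randomisation already deals with this. Allocation is random and follows surgery, so the unadjusted comparison is unbiased and its 5% error rate includes the effect of chance imbalance. That stands. A reader might infer that a baseline gap would simply be taken for a treatment effect, and might cite the 29% chance of a gap beyond 0.3 SD. The working does not bear this out: at a 0.3 SD gap the conditional false-positive rate is still about 5%. Only at gaps near 0.5 SD, exceeded in about 8% of trials, does it reach 7 to 11%.

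The gain is also modest. The outcomes are secondary, and the trial remains underpowered for a 0.5 SD difference with or without adjustment. That stands too. It argues for treating this as an inexpensive improvement, not as a flaw that invalidates results.

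Three other stronger readings go beyond the documents:

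- That only the 18 comparisons are affected. No outcome has a listed pre-operative value. The week-2 pain and motion values are post-operative, and the protocol does not say they precede heel walking.
- That the comparisons cannot be corrected. The protocol is silent on pre-operative collection and does not exclude it, and other pre-surgical covariates could be used. What is missing is a planned adjustment and a listed starting score.
- That a week-2 FAOS would sit near the floor and so be useless. The questionnaire looks back one week, which at week 2 falls while the bulky dressing is still on. It would therefore describe early recovery more than the patient's pre-operative level, but no data in the documents show how low the scores would be.

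**Conclusion.** The point holds as one of precision and interpretability, not of bias. No outcome has a listed pre-operative value and only unadjusted tests are planned. FAOS and AOFAS are the worst placed, with no value of any kind until the period of differing regimens has passed.

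The size depends on the assumed correlation of 0.3 to 0.5: a gain worth roughly 2 to 8 patients per arm (27.5 − 25 to 33.3 − 25) and 4 to 11 percentage points of power at 0.5 SD. The count of 18 of 38 depends on one test per score per visit. The link to quality of life is narrower than the count suggests: that subscale accounts for 3 of the 18 comparisons.

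The change is worth making because it needs no extra patients and because a pre-operative score cannot be recovered once surgery has taken place.

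**What to change.** In Study outcomes, add a pre-operative assessment of FAOS, AOFAS, VAS pain at the three sites and range of motion, and state when it is done. Because randomisation follows surgery, any such value precedes allocation and is a valid covariate.

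In Statistical analysis, replace the unadjusted test for each later score with ANCOVA, with arm as the factor and the pre-operative value of the same score as covariate. Report the adjusted difference with its 95% confidence interval. If pre-operative values are already recorded in routine care, the change is one of wording only.

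The cost is one questionnaire and one examination per patient. The protocol lists no pre-operative visit, so that contact has to be named. Any patient already enrolled without a baseline needs mean imputation of the covariate or a missing-baseline indicator, and the plan should say which.

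### Cheap improvement, not an error: pre-specify adjustment of HVA and IMA for the pre-operative film, and say which film radiological 'changes' are measured from

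*Combined protocol and SAP*

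**What the plan says.** The Statistical analysis section of the combined protocol and SAP is one paragraph. For comparing the arms it states: "Between-group comparisons will be conducted by one-way analysis of variance (continuous normal distributed data), Mann-Whitney U test" for non-normal continuous data, "or chi-square test (categorical data) depending on the type and distribution of data". No covariate, ANCOVA, mixed model or use of a baseline value appears there or elsewhere.

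Study outcomes opens its definition of the primary outcome with the two angles: "Radiological changes including hallux valgus angle (HVA), intermetatarsal angle (IMA". The third component and the timing of the films come next: "tibial sesamoid position by weight bearing feet X-Rays will be measured at 12, 18, and 26 weeks post-surgery". It does not say what the changes are measured from. No pre-operative film is listed, and the follow-up visits in the Patients section are all post-operative. The scale for tibial sesamoid position is not given.

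Two further statements bear on the point. The radiological hypothesis is that early walking "will not negatively affect the stability of the surgical reconstruction correction". The Patients section says "Randomization will be performed after the end of the EDSTP surgery", with 25 patients per arm.

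**The concern.** HVA and IMA at follow-up may depend in part on how severe the deformity was before surgery. There are two natural readings of 'changes', and the planned tests handle severity differently under each:

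- If follow-up values are compared, differences in pre-operative severity stay in the error term.
- If change from a pre-operative film is compared, severity is subtracted with a fixed slope of 1, which adds noise when the true slope is well below 1.

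Both comparisons are unbiased in a randomised trial. What is at stake is the width of the interval for the arm difference. That width matters here because the radiological claim is one of no harm, and such a claim is only as informative as its interval. Leaving the reference film unstated also leaves open which quantity will be analysed.

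**Working it through.** **Inputs.** From the documents: 25 per arm, N = 50, two-sided 0.05. Not in the documents, so assumed: the pre/post correlation r, and k = pre-operative SD divided by follow-up SD. The follow-up SD is set to 1. No dropout rate is given, so all 50 are taken as analysed first, then 44 to 36.

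**The plan's own figure.** 2 × 25 = 50 checks, but there is no power calculation to reproduce. For orientation, 25 per arm gives 80% power for a difference of 0.81 SD (noncentral t).

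**Unadjusted follow-up values.** With two arms, one-way ANOVA is the t-test. The 95% CI half-width is t(48) × √(2/25) = 2.011 × 0.283 = 0.569 SD.

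**ANCOVA against follow-up values (one visit, linear model).** The variance ratio is (1 − r²) × (N − 3)/(N − 4) = (1 − r²) × 47/46. The factor 47/46 = 1.022 is the price of estimating the slope.

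| r | Variance ratio | CI half-width (SD) |
|---|---|---|
| 0 | 1.022 | 0.575 |
| 0.2 | 0.981 | 0.564 |
| 0.3 | 0.930 | 0.549 |
| 0.5 | 0.766 | 0.498 |
| 0.7 | 0.521 | 0.411 |

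The half-width uses t(47) = 2.012; at r = 0, for example, 2.012 × 0.283 × √1.022 = 0.575. A simulation of 100,000 trials per value gave variance ratios of 1.023 at r = 0, 0.931 at r = 0.3 and 0.765 at r = 0.5. At the 0.81 SD difference, power moves from 80% to 79.1%, 82.7% and 89.2% at r = 0, 0.3 and 0.5.

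**Break-even.** Setting (1 − r²) × 47/46 = 1 gives r = √(1/47) = 0.146. On CI width, which also counts the lost degree of freedom, it is 0.150. With 44 analysed it is √(1/41) = 0.156 (0.161 on width). With 36 it is √(1/33) = 0.174 (0.180 on width).

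**ANCOVA against unadjusted change scores.** The variance of a change score is 1 + k² − 2rk, so the ratio is (1 − r²)(47/46)/(1 + k² − 2rk).

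| k | r = 0.2 | r = 0.3 | r = 0.5 | r = 0.7 |
|---|---|---|---|---|
| 0.75 | 0.777 | 0.836 | 0.943 | 1.017 |
| 1 | 0.613 | 0.664 | 0.766 | 0.869 |
| 1.5 | 0.370 | 0.396 | 0.438 | 0.453 |

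Because 1 + k² − 2rk = (1 − r²) + (k − r)², this ratio can never exceed 47/46. The worst loss in variance is therefore about 2% under either reading of 'changes'.

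**Why the reading stops mattering.** Write follow-up as Y, pre-operative value as X and arm as A. If Y = a + bA + cX + error, then Y − X = a + bA + (c − 1)X + error. The arm effect b is the same. This needs a linear model and the same film; it does not hold for rank or ordinal methods or for percentage change.

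**The case against.** The strongest reply is that nothing here is wrong. The planned tests are valid, no passage contradicts another, and the gain rests on an r that the documents do not supply. Surgery lies between the films, so r may well be low. At r = 0.2 the half-width falls only from 0.569 to 0.564 SD, and at r = 0 it rises. The larger gains need r of 0.5 to 0.7, which the documents do not support. All of this stands, and it is why the point is an improvement and not an error. What remains is the lopsided trade: about 2% of variance at worst, against a gain that could be substantial.

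Three limits also stand. The low cost depends on a pre-operative weight-bearing film that the documents do not schedule. The 0.15 threshold applies to the comparison with follow-up values and rises with attrition. The variance factors belong to the linear model and do not carry over directly if the angles are tested by Mann-Whitney.

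A reader might infer more than the documents support:

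- *That the unadjusted analysis is biased or invalid.* It is not; allocation is randomised.
- *That sesamoid position will be tested by chi-square, with a known loss of power.* The plan chooses the test by data type and distribution and never assigns this outcome to chi-square. It does not say that position is graded. Any power figure would need an assumed number of grades, their frequencies and an effect size.
- *That a narrower interval would establish that early walking does no harm.* No margin is stated, so precision alone cannot settle that.

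**Conclusion.** The point holds as a cheap improvement centred on HVA and IMA. Pre-specified adjustment for the pre-operative value would reduce the variance of the arm difference by about 7% at r = 0.3 and 23% at r = 0.5 relative to follow-up values, and would cost about 2% at r = 0. Relative to change scores with equal SDs, the reduction is 34% at r = 0.3 and 23% at r = 0.5; with a pre-operative SD of 0.75 of the follow-up SD and r = 0.7 there is a 2% loss.

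These sizes assume a linear model, 25 analysed per arm and a usable pre-operative film for each patient. The actual gain is unknown because r is unknown. The benefit that does not depend on r is clarity: for HVA and IMA, the undefined reference for 'changes' would no longer affect the arm comparison.

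**What to change.** 1. In Study outcomes, name the pre-operative weight-bearing film as the reference, and record HVA and IMA from it. It precedes randomisation, so it is a legitimate covariate.
2. In Statistical analysis, pre-specify ANCOVA for HVA and IMA, or a mixed model over 12, 18 and 26 weeks (arm, visit, arm by visit), with the pre-operative value as covariate. Report the adjusted arm difference with a 95% CI. Fix the model in advance, not after inspecting the distribution.
3. State the scale of tibial sesamoid position. If it is recorded as ordered grades, use an ordinal model with the pre-operative grade, or at least Mann-Whitney, and not chi-square.

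**Cost.** A few sentences of statistical wording, the recording of pre-operative measurements, and one degree of freedom. No visit is added if the film is already part of the surgical work-up. If it is not, a film would have to be added and the change is no longer cheap.

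### Every outcome is measured at three or five visits, but the plan names no visit, contrast or longitudinal model, so faster recovery has no prespecified test

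*Combined protocol and SAP*

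**What the plan says.** Under Hypothesis and study objectives, the plan expects that early weight bearing "allows faster rehabilitation with better 1MTPJ range of motion and faster decrease in generalized swelling". It also expects better quality of life and a radiological correction that is not made worse.

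Under Study outcomes, every outcome is repeated:
- The radiographic primary outcome has three visits: "tibial sesamoid position by weight bearing feet X-Rays will be measured at 12, 18, and 26 weeks post-surgery". AOFAS and FAOS follow the same three visits.
- Range of motion has five: "Range of Motion (ROM) at 1MTPJ will be measured at 2, 6, 12, 18, and 26 weeks post-surgery". Pain has the same five.

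Under Statistical analysis, continuous outcomes get: "Between-group comparisons will be conducted by one-way analysis of variance (continuous normal distributed data". The alternatives are "Mann-Whitney U test (continuous non-normally distributed data), or chi-square test (categorical data) depending on the type and distribution of data". The decision rule is: "All hypotheses are two-tailed, and p values <0.05 are considered statistically significant".

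No section names a primary visit, a summary over visits, an arm-by-visit term, an area under the curve, a time-to-recovery endpoint, a baseline covariate, a missing-data method or a multiplicity rule.

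**The concern.** Part of the hypothesis concerns how soon patients recover. The listed tests compare two arms on one value per patient. The plan does not say which of the three or five values is used, or how they are combined. The natural use is one test per visit, and then a claim of faster recovery can rest on any visit that falls below 0.05. The trial is open-label, so this choice should be closed before results are seen.

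Two further costs follow. A per-visit test discards patients who missed that visit even when their other readings are available. A test at one visit also makes no use of the patient's other readings, in a trial with 25 patients per arm.

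**Working it through.** **Inputs from the documents.** 25 per arm ("Parallel groups will be allocated at 1:1 ratio via a computer generated random number, with 25 patients at each group"); two-sided 0.05 at each test; three visits (weeks 12, 18, 26) or five (weeks 2, 6, 12, 18, 26). The plan gives no power, effect size, SD or dropout rate for its 50 patients, so there is no figure of its own to reproduce.

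**Inputs assumed.** Between-visit correlation rho, equal for all pairs of visits: 0.6 to 0.8, with 0.3 as a low case. 20% missing at week 26, for illustration only.

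**1. False positives if each visit is tested.** With independent visits the chance of at least one is 1 - 0.95^3 = 14.3% for three and 1 - 0.95^5 = 22.6% for five. Correlation lowers it. Simulating two-sample tests with 25 per arm and no true difference at any visit gives:

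| rho | three visits | five visits |
|---|---|---|
| 0.3 | about 14% | about 21% |
| 0.6 | about 12% | about 17% |
| 0.8 | about 10% | about 13% |

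These are per outcome, before counting several outcomes.

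**2. Detectable effect at one visit.** (1.96 + 0.84) x sqrt(2/25) = 0.79 SD at 80% power, or 0.81 SD with the t distribution.

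**3. Average of weeks 12, 18 and 26.** Variance relative to one visit is (1 + 2 rho)/3.
- rho 0.6: 0.733, square root 0.856; 0.81 x 0.856 = 0.69 SD.
- rho 0.8: 0.867, square root 0.931; 0.81 x 0.931 = 0.75 SD.

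The square roots are also the break-even points. Averaging beats week 26 alone only if the mean arm difference is at least 86% (rho 0.6) to 93% (rho 0.8) of the week-26 difference. If the difference grew as 0, half, full over the three visits, the mean would be 50% of the week-26 value. The detectable week-26 effect would then be 0.69/0.5 to 0.75/0.5, about 1.4 to 1.5 SD, worse than 0.81.

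**4. One visit, same contrast.** With complete data and no covariate, a mixed model with a free mean for each arm and visit has the same standard error as the per-visit test: sqrt(2/25) = 0.283 SD.

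**5. Missing data.** With 20 of 25 per arm seen at week 26 and all seen earlier, effective n is 1/[(1 - rho^2)/20 + rho^2/25], using one earlier value.
- rho 0.6: 1/(0.0320 + 0.0144) = 21.6 per arm.
- rho 0.8: 1/(0.0180 + 0.0256) = 22.9 per arm.

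The per-visit test keeps 20.

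**6. Adjusting for one earlier value.** Variance is multiplied by 1 - rho^2, which is 0.64 at rho 0.6 and 0.36 at rho 0.8.

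**The case against.** The strongest reply is that the named tests are sound and the choice of model is largely preference. Each patient gives one value per visit, so a per-visit comparison is valid. Range of motion and pain are measured at week 6, and an arm comparison there bears directly on earlier recovery. A mixed model that printed a p value at every visit would have the same multiplicity. All of this stands: the gap is the missing visit or contrast, and naming one cures the multiplicity under either method.

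It also stands that the radiological hypothesis is about maintaining correction, not speed. There the more serious error is wrongly concluding no harm, which the false-positive figures do not measure. The plan's background fears recurrence, which could build up over time, so an equal arm difference at weeks 12, 18 and 26 cannot be taken for granted.

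A reader might infer that repeated readings will be stacked as independent rows, which would invalidate the tests. The plan does not state that use, so the point does not rest on it. A reader might also infer that a better model would test the whole hypothesis. It would not: swelling is not a listed outcome, and FAOS quality of life is first measured at week 12.

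What the reply does not remove is that, as written, no comparison is designated as the test of faster recovery.

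**Conclusion.** The point holds as a gap in prespecification with a modest efficiency cost, and should be corrected. If each visit is tested as the section allows, the false-positive chance per outcome is about 10-12% (three visits) or 13-17% (five) instead of 5%, at assumed correlations of 0.6 to 0.8. At 0.3 it is about 14% and 21%. The direction holds throughout this range; only the size changes.

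The precision gain is conditional. The three-visit average lowers the detectable effect from 0.81 to 0.69-0.75 SD only if the arm difference is about constant across visits. For a single visit with complete data and no covariate there is no gain. The documents do not support saying that the listed tests are invalid, or that they could never bear on early recovery.

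**What to change.** For each continuous outcome (HVA, IMA, range of motion, pain, AOFAS, FAOS subscales), prespecify one mixed model for repeated measures with arm, visit and arm-by-visit. Name one contrast per outcome as its only significance test:
- **Pain and range of motion:** an early contrast such as the arm difference at week 6, with the week-2 value as covariate if it is taken before heel walking starts in the trial arm.
- **HVA and IMA:** either week 26, or the week 12-26 average if a roughly constant arm difference is expected. Choose one in advance and give the reason.
- **AOFAS and FAOS:** one named visit or average, chosen in the same way.

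Adjust for the pre-operative value where it is recorded. The outcome schedule lists no pre-operative measurement, so the sponsor should confirm which exist. Report other visits as estimates with 95% CI. Analyse tibial sesamoid position with an ordinal method if it is graded. Either add a swelling measure or drop swelling from the hypothesis.

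The analysis changes need SAP wording and a little more analysis work, with no extra patients or visits. Only a swelling measure, or a pre-operative value not already recorded, would add data collection. The downsides are normality, missing-at-random and covariance assumptions (an unstructured matrix over five visits has 5 x 6/2 = 15 parameters, from 50 patients), and a changed estimand if the average is chosen.
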